### 6.2 TEST TREATMENT

Test treatment for this trial is defined as DA-9805 45mg or 90mg. DA-9805 is an oral tablet that will be taken three times daily during this study.

- Group 1: DA-9805 45mg tablet (15 mg TID)
- Group 2: DA-9805 90mg tablet (30 mg TID)
- Group 3: placebo tablet (0 mg DA-9805 TID)

The ingredients in each DA-9805 tablet are included in [Table 6-1](#) below.

### 6.3 CONTROL TREATMENT

The control treatment is Placebo, which will look, and will be packaged and maintained exactly the same way as the test treatment. The ingredients in each placebo tablet are included in [Table 6-1](#).

**Table 6-1: Study Treatment Ingredients**

	Ingredient(mg/tablet)	DA-9805 45mg (15mg TID)	DA-9805 90mg (30 mg TID)	Placebo 0mg (0mg TID)
	Moutan Root Bark · Bupleurum Root · Angelica Dahurica Root (1:1:1) 90% Ethanol Soft Extract	15	30	0
	Copovidone	2.5	2.5	2.5
	Magnesium Aluminometasilicate	20	40	20

Lactose Hydrate	39	21.5	39
Microcrystalline Cellulose	39	21.5	54
Croscarmellose Sodium	7.5	7.5	7.5
Magnesium Stearate	2	2	2
Opadry White	3.75	3.75	3.75
Opadry Pink	5	5	5
Carnauba Wax	0.05	0.05	0.05
Total weight	133.8mg	133.8mg	133.8mg

#### **6.4 STUDY TREATMENT LABELING AND PACKAGING**

Both DA-9805 and placebo tablets will be provided under appropriate investigational product labeling. For the Double-Blind phase of the study, investigational product will be provided as blister packs. Each blister pack will contain 10 tablets of DA-9805 or placebo.

#### **6.5 STUDY TREATMENT STORAGE**

All study treatments will be stored at temperatures up to 25°C and protected from direct light (Storage: Up to 25°C ). Access to study treatment will be restricted to authorized personnel only.

#### **6.6 STUDY TREATMENT ADMINISTRATION**

All subjects, after signing the Informed Consent Form (ICF), will be assessed during the screening phase. Eligible subjects who have completed the screening phase will proceed with randomization and the double-blind treatment phase of the study.

- Subjects randomized to the active treatment groups (45mg or 90mg) will take one tablet three times daily with water.
- Subjects randomized to the Placebo treatment group will take one Placebo tablet three times daily with water.

Placebo tablets, as described in [Section 6.3](#) will be identical in appearance to the DA-9805 tablets.

#### **6.7 STUDY TREATMENT DISPENSATION**

At Treatment Visits 0, 1 and 2 of the study, sufficient randomized study treatments will be dispensed to each randomized subject for the period of time between the current clinic visit and the next clinic visit. Investigational products will be provided as blister packs. Each blister pack will contain 10 tablets of DA-9805 or placebo. For the active treatment group, 11 blister packs of active tablets (DA-9805 45mg or DA-9805 90mg as per treatment assignment) will be dispensed at each of these visits. For the placebo group, 11 blister packs of placebo tablets will be dispensed at each of these visits.

## **6.8 STUDY TREATMENT ACCOUNTABILITY**

The Investigator or designee will verify the contents of each shipment against the shipping documents. Verification of study treatment receipt will be documented according to the Sponsor's requirements.

A study treatment accountability log will be provided to the site for use by the Investigator to maintain current and accurate inventory records (batch, expiry, and quantity) covering the receipt, dispensing and the destruction of all the study treatments.

At the conclusion of the study, or other situations as applicable (ex. site closure, IP expiry, etc.) the Investigator must agree to return or destroy all study materials as instructed by the Sponsor.

## **6.9 STUDY DRUG COMPLIANCE**

Subjects will be instructed to bring used/unused study treatment blister packs. At each of these visits, tablet counts of returned study treatments will be conducted to determine if the subject has taken the study treatment per the protocol. If the number of dispensed tablets minus the number of remaining tablets (<80%) indicates that the subject is not taking their study treatment according to the study protocol, this will be recorded as a study drug non-compliance and the subject will be re-instructed on proper dosing. If the subject continues to be non-compliant with the dosing regimen the subject might be withdrawn from the study per the PI and/or the Sponsor's discretion. During Visits 1 to 3 subjects are required to report the date and time for the last daily dose of study treatment taken since the last visit.

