**Figure 3-1: Study Flow Diagram**

### 3.1 STUDY POPULATION

#### 3.1.1 NUMBER OF SUBJECTS

A total of 60 subjects will be randomized to this study from up to 10 Centers within the USA.

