#### **4.1.3 TREATMENT VISIT 1 (TV1) (WEEK 4: DAY 28±3), TREATMENT VISIT 2 (TV2) (WEEK 8: DAY 56±3), TREATMENT VISIT 3 (TV3) (WEEK 12: DAY 84±3)**

The following assessments will be performed:

- Vital signs (Refer to [Section 8.5](#))
- Weight and BMI (Refer to [Section 8.6](#)) (Only at TV3)
- Physical examination (Refer to [Section 8.7](#))
- Laboratory assessments (hematology, biochemistry and urine analysis) (Refer to [Section 8.8](#))
- Electrocardiogram (Refer to [Section 8.9](#)) (This is done ONLY at TV1 and TV3)
- Urine pregnancy test (Refer to [Section 8.10](#)) (This is done ONLY at TV3)
- MDS-UPDRS Scale (Refer to [Section 8.11](#))
- Hoehn and Yahr (H&Y) Scale (Refer to [Section 8.12](#))
- Schwab and England (S&E) Scale (Refer to [Section 8.15](#))
- Parkinson's Disease Questionnaire (PDQ-39) total score (Refer to [Section 8.13](#))
- Clinical Global Impression-Severity (CGI-S) and Clinical Global Impression-Improvement (CGI-I) scale (Refer to [Section 8.16](#))
- List concomitant medications (Refer to [Section 7](#))
- Columbia-Suicide Severity Rating Scale (C-SSRS) (Refer to [Section 8.16](#))
- Adverse events evaluation (Refer to [Section 10](#))
- Study treatment dispensation (This is done ONLY at TV1 and TV2) (Refer to [Section 6.7](#))
- Study treatment accountability (Refer to [Section 6.9](#))

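### Does the unstated denominator of the 80% tablet-count threshold in protocol 6.9 call for a change to the plan?

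*Protocol*

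**What the plan says.** Protocol 6.9 has used and unused blister packs returned and counted at the visits, "to determine if the subject has taken the study treatment per the protocol". The rule then begins: "If the number of dispensed tablets minus the number of remaining tablets (<80%) indicates that the subject is not taking their study treatment". A subject caught by it is recorded as non-compliant and re-instructed. If the problem persists, the investigator and/or the sponsor may withdraw the subject at their discretion. The same section adds: "During Visits 1 to 3 subjects are required to report the date and time for the last daily dose of study treatment".

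The related quantities are in neighbouring sections. In protocol 6.6 subjects on active treatment "will take one tablet three times daily with water", and placebo subjects follow the same pattern. In protocol 6.7, "Each blister pack will contain 10 tablets of DA-9805 or placebo" and "For the placebo group, 11 blister packs of placebo tablets will be dispensed at each of these visits"; the active arms also receive 11 packs per visit. Treatment visits are four weeks apart, each with a window of 3 days either way (protocol 3 and 4.1.3).

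Protocol 9.9.5 and SAP 8.1.6 provide only for descriptive summaries and/or listings of compliance. SAP 7.9 gives formulas for age, height, weight, BMI and change from baseline, but none for compliance.

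**The concern.** A threshold without a denominator is not a complete rule. The sentence names two counts, dispensed and remaining, so a literal reader could divide the difference by the number dispensed. Because the supply exceeds what the regimen uses, that reading would mark a subject who missed no dose as non-compliant at an on-time visit.

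Protocol 3.1.1 allows up to 10 centers. If they chose different bases, the same count could be recorded as compliant at one and non-compliant at another, and the SAP output would not show which percentage it holds. In a first-in-human study whose primary objective is safety and tolerability, one would not want correctly dosing subjects told otherwise. A run of false flags might also lead to withdrawals or, if someone treated them as major violations, to exclusions from the per-protocol (PP) set used for the primary efficacy analysis.

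**Working it through.** The plan gives no worked compliance percentage, so there is no figure to reproduce. The check compares the possible bases.

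**Inputs.** Tablets dispensed per visit: 11 x 10 = 110 (protocol 6.7). Tablets prescribed per day: 3 (protocol 6.6). Interval: 28 days nominal. TV0 to TV1 can run 25 to 31 days. Later intervals have a window at both ends and can run 22 to 34 days. Assumption: three tablets on every elapsed day.

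**Formulas for a fully adherent subject.** Dispensed base: 3 x days / 110. Prescribed base, actual days: 3 x days / (3 x days). Prescribed base, fixed four weeks: 3 x days / 84.

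| Days | Tablets taken | Of 110 dispensed | Of 3 x days | Of fixed 84 |
|---|---|---|---|---|
| 22 | 66 | 60.0% | 100% | 78.6% |
| 25 | 75 | 68.2% | 100% | 89.3% |
| 28 | 84 | 76.4% | 100% | 100% |
| 29 | 87 | 79.1% | 100% | 103.6% |
| 30 | 90 | 81.8% | 100% | 107.1% |
| 31 | 93 | 84.5% | 100% | 110.7% |
| 34 | 102 | 92.7% | 100% | 121.4% |

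**Where the readings part.** On the dispensed base the cut-off is 0.8 x 110 = 88 tablets, or 88/3 = 29.3 days of full dosing. Perfect adherence is therefore flagged at 29 days or less and passes at 30 or more. Over 28 days the prescribed cut-off is 0.8 x 84 = 67.2, so counts of 68 to 87 tablets are classified in opposite ways. The two prescribed versions agree for a fully adherent subject except at the extreme 22-day interval (66/84 = 78.6%; at 23 days, 69/84 = 82.1%).

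**Which reading the text supports.**
- In 6.9 the purpose of the count, the trigger, the re-instruction and the description of continued failure all refer to the protocol or its dosing regimen. Dispensed minus remaining is the ordinary way to obtain tablets taken; it is a numerator and need not imply the base.
- The 110 behaves like a supply figure. The longest permitted interval needs 3 x 34 = 102 tablets; ten packs (100) would fall short and eleven cover it.
- On the dispensed base, passing at day 28 takes 88 tablets, against 84 in the regimen. A rule meant to detect under-dosing would then be met only by exceeding the regimen by 4 tablets.

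**What depends on the answer.**
- Compliance is not among the efficacy or safety outcomes (protocol 9.2, SAP 3).
- The PP definition (protocol 9.8.2, SAP 6.2) excludes major protocol violations and does not mention the 80% figure. The deviation categories in SAP 8.1.2 do not name tablet counts, although the last category is open-ended. PP membership is fixed before database lock and unblinding.
- All three arms receive the same number of tablets, so the supply itself would not make any misclassification differ by arm.
- If the tablet counts and visit dates are in the database, any of these percentages can be recomputed.

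**The case for a change.** The best case for a change is that an operational rule used at several centers should not rest on inference. The literal arithmetic of 6.9 is available to anyone, it gives the wrong-looking answer at the scheduled visit itself, and even the prescribed base has two versions. One sentence in each document would settle it, with no new data.

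Much of this stands. The denominator is missing from both documents, the 76.4% against 100% contrast is correct, and actual days versus a fixed 84 is a real, though minor, further choice.

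Three parts do not carry the weight placed on them. First, divergence between sites is a possibility and is not shown; the CRF and the Data Management Plan mentioned in protocol 15.2 are not among the documents and may or may not define the calculation. Second, a whole-course version of the problem (243/330 = 73.6% at Day 81 to 261/330 = 79.1% at Day 87) assumes a cumulative test, whereas 6.9 describes counts at each visit. Third, protocol 6.6 and 6.7 do not conflict: one states the regimen and the other a supply with a margin. Only 6.9 lacks a term.

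**Conclusion.** The gap is real, but no change to the plan follows. It is an unwritten definition that sites and analysts would very likely fill with tablets required by the regimen, because the wording leans that way and the alternative flags perfect adherence at the nominal visit. If a site did divide by tablets dispensed, a fully adherent subject would score 76.4% at 28 days and be flagged at any interval of 29 days or less. The documented result would be a non-compliance record and re-instruction, with withdrawal only by discretion if it continued. No endpoint or population rule uses the percentage, so the trial's results and conclusions do not turn on it.

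This rests on three assumptions: dosing is counted as three tablets per elapsed day; tablet counts and dates are captured so that the percentage can be derived centrally; and the 80% figure is not used to decide PP membership. The documents give it no such role. What the sponsor intends as the base is for the sponsor to say, and nothing here questions the dose, the threshold or the withdrawal wording.

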## 7 CONCOMITANT AND PROHIBITED MEDICATIONS

Initiation of any new Parkinson's treatment during the study is prohibited.

Subjects must be questioned at each study visit concerning any new medications or changes in current medications including over-the-counter medication and topical medication. All medications and therapies administered or taken by the subject beginning 30 days prior to signing the ICF and throughout the study will be recorded in the source documents and on the appropriate page of the CRF.

For each medication and non-study treatment, the following will be documented:

- Medication/treatment name (generic name may be used if trade name is unknown)
- Dose, unit, and frequency of dosing (individual dosages, not total daily dose). Note: Each new dose of medication should be recorded as a separate entry, with the exception of medications that are given on a sliding scale. For these, it is acceptable to enter the range of the dosage, including the start and stop dates for which the specified dosage range was used.
- Route of dosing
- Indication for use
- The start date
- The stop date (if medication/therapy is not ongoing)

### 7.1 PROHIBITED MEDICATION

The following treatments and medications are prohibited throughout the study

1. Initiation of any anti-parkinsonian medication (including levodopa, dopamine agonists, entacapone and monoamine oxidase-B inhibitors) for the duration of the trial.
2. Initiation of Amantadine or anticholinergics for newly diagnosed subjects or change in the dosage of Amantadine or anticholinergics during the trial for subjects who were on stable doses for 4 weeks prior to screening.

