### 1.3 DA-9805

DA-9805 is a botanical drug product composed of three main raw herbal materials; Moutan Root Bark [MC], Bupleurum Root [BF] and Angelica dahurica root [ADR]. The main active ingredients are Paeonol, Saikosaponin A and Imperatorin respectively. All the three herbal raw materials are listed in the Japanese, Korean and Chinese Pharmacopoeias. DA-9805 reduces neuronal loss by:

1. Protection of MPTP (1-methyl-4-phenyl-1,2,3,6-tetrahydropyridine) induced nigrostriatal dopamine neuron degeneration.
2. Restoration of 6-OHDA (neurotoxin 6-hydroxydopamine) induced nigrostriatal dopamine neuron degeneration.
3. Inhibition of Rotenone induced  $\alpha$ -synuclein accumulation in substantial niagra (SN).
4. Inhibition of LPS induced microglial/astrocyte activation in substantial niagra/striatum(ST).

It is expected that DA-9805 will help treat PD by prevention of dopaminergic neurodegeneration via recovery of mitochondrial dysfunction, anti-inflammatory effect and relief from Endoplasmic reticulum (ER) stress and oxidative stress.

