### 1.4 SUMMARY OF PRIOR PRE-CLINICAL STUDIES

The botanical components of DA-9805 (Moutan Root Bark [MC], Bupleurum Root [BF] and Angelica dahurica root [ADR]) have a long history of human use and have been tested individually and in various combinations in animal models. Based on available published information, MC has been attributed anti-depression, prevention of dementia, improvement of cognitive functions, and anti-inflammatory, neuroregenerative, anti-oxidant, anti-cancer and hypoglycemic effects. Similarly, BF is attributed therapeutic effects in brain damage and depression, and has also shown neuroprotective, neuroregenerative, anti-cancer, anti-allergy effects. Based on published literature, ADR is attributed anti-depression, prevention of dementia, improvement of cognitive function and anti-inflammatory, antioxidant and anti-asthmatic effects.

All three botanicals listed in KP, Chinese Pharmacopoeia (CP) and Japanese Pharmacopoeia (JP) as well as other pre-existing oriental medicine books as over-the-counter (OTC) medicines and approved drugs in Korea, China and Japan. However, none of these consist of individual components of DA-9805 alone, but rather a various combinations with other botanicals. DA-9805 will be the first botanical mixture comprising of all three botanical ingredients.

In addition to Korea, China and Japan, MC, BF and/or ADR containing products can also be found in US, Canada, Australia, Taiwan, Europe and Southeast Asia. These products are not only available as prescription drugs, but also as herbal OTC medicinal products and dietary/food supplements. MC containing products have been used in central nervous system disorders, indigestion, cough, dental care, anemia, and constipation, among other indications. BF containing products have been used in headache, cold, insomnia, enterogastritis, constipation, neurosis and other indications. Finally, ADR containing products are used in fever, headache, antiemetic, cold, insect bites, rhinitis and other indications.

The current market status on products that contain MC, BF and ADR, individually or in combination, in various countries is briefly summarized below.

- In Korea, there are hundreds of products containing MC (115), BF (162) or ADR (67), which are all approved and released as medicinal products by MFDS. MC, BF or ADR are prohibited as raw materials for food in Korea.

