- In China, MC, BF or ADR are approved as raw materials for health food and they are found in many of the nutritional products that are approved by the China Food and Drug Administration. The Chinese Pharmacopoeia has listed 29, 22 and 47 regulated products of Traditional Patent Medicine containing MC, BF and ADR, respectively.
- In Japan, out of the 233 common herbal prescriptions and 148 medicinal herbal prescriptions approved by the government, MC is found in 18 products, BF is found in 38 products and ADR is found in 18 products.
- In Taiwan, out of the 200 Chinese medicinal prescriptions listed in the Taiwan Herbal Pharmacopoeia, 12 products contained MC, 25 products contained BF and 14 products contained ADR.
- In US, there are some dietary supplements that contain MC, BF or ADR but they have not been registered or regulated.
- In Canada, MC, BF and ADR are listed as acceptable traditional Chinese medicine ingredients for natural health products in Canada. Traditional Chinese medicine (TCM) products containing MC, BF or ADR are registered marketed as dietary supplements in Canada by various Chinese pharmaceutical companies.
- In Australia, traditional Chinese medicine (TCM) products containing MC, BF or ADR are registered and marketed as complementary medicine by various Chinese pharmaceutical companies.
- In Southeast Asia, countries such as Vietnam, Malaysia, Singapore and Indonesia allow imports of TCM products containing MC, BF or ADR from China.
- In Hong Kong, there are some traditional medicinal products and foods containing MC, BF and ADR.
- In Europe, a few traditional Chinese patent medicines containing MC and ADR are marketed in England and Belgium as dietary supplements.

Dong-A conducted a number of nonclinical studies with DA-9805 and its individual botanical components, as well as with proposed purified active ingredients. Dong-A DA-9805 nonclinical studies were conducted in compliance with the Ministry of Food and Drug Safety (MFDS) (Notification No. 2013-232 'The Standards of Pharmacology Study for Medicinal Products' [Oct 30, 2013] and Notification No. 2014-67 'Good Laboratory Practice [GLP]' [Feb 12, 2014]) and Organization for Economic Co-operation and Development (OECD) GLP requirements and also comply with the current International Conference on Harmonization (ICH) guidelines, including ICH guideline S7A 'Safety Pharmacology Studies for Human Pharmaceuticals' (Nov 08, 2000).

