### 3.1.3 EXCLUSION CRITERIA

Subjects will be eligible for enrollment in the study only if they meet NONE of the following criteria:

1. Subject has an atypical parkinsonian syndrome or secondary parkinsonism (e.g., due to drugs, metabolic neurogenetic disorders, encephalitis, cerebrovascular disease or degenerative disease).
2. Subjects with history of neurosurgical intervention for Parkinson's disease.
3. Subjects who meet the DSM-V criteria at screening for bipolar disorder, major depressive disorder, psychotic disorders, or any other comorbid mental disorders that in the opinion of the Investigator may interfere with study conduct and results interpretation.
4. Subjects with clinical diagnosis of dementia (MMSE score  $<24$ ) as determined by the investigator using Mini-Mental State Examination (MMSE).
5. Female subjects who are pregnant or breast feeding.

6. Initiation of any anti-parkinsonian medication (including levodopa, dopamine agonists, entacapone and monoamine oxidase-B inhibitors) for the duration of the trial.
7. Initiation of Amantadine or anticholinergics for newly diagnosed subjects or change in the dosage of Amantadine or anticholinergics during the trial for subjects who were on stable doses for 4 weeks prior to screening.
8. Subjects who used investigational drugs or devices within 60 days prior to screening or investigational biologics within the last 6 months prior to screening.
9. Subjects with a clinically significant medical or surgical condition, including major surgeries within 28 days prior to enrollment.

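### Protocol 1.4 says US supplements contain the botanicals in DA-9805, but the eligibility and prohibited lists do not address them, so use for a non-Parkinson's reason breaches no written rule

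*Protocol*

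**What the plan says.** **Product and market.** Protocol 1.3 describes DA-9805 as a botanical product made from Moutan root bark (MC), Bupleurum root (BF) and Angelica dahurica root (ADR). Section 1.4 lists the US among the places where products with MC, BF and/or ADR are found. It says of such products: "These products are not only available as prescription drugs, but also as herbal OTC medicinal products and dietary/food supplements". For the US it adds: "In US, there are some dietary supplements that contain MC, BF or ADR but they have not been registered or regulated". Section 3.1.1 places every site there: "A total of 60 subjects will be randomized to this study from up to 10 Centers within the USA".

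**Restrictions.** Section 7.1 opens with "The following treatments and medications are prohibited throughout the study" and has two items. The first is "Initiation of any anti-parkinsonian medication (including levodopa, dopamine agonists, entacapone and monoamine oxidase-B inhibitors) for the duration of the trial". The second concerns starting amantadine or anticholinergics, or changing their dose. Section 7 also opens with a bar on starting a new treatment for Parkinson's disease. Inclusion 3 limits current Parkinson's medication to stable amantadine or anticholinergics. Exclusion 8 covers "Subjects who used investigational drugs or devices within 60 days prior to screening" and investigational biologics. No entry criterion names herbal products, supplements or any of the three botanicals.

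**Recording and analysis.** Section 7 has subjects asked at each visit about "any new medications or changes in current medications including over-the-counter medication and topical medication". It also requires all medications and therapies from 30 days before consent onward to be documented. SAP 8.1.4 codes, summarises and lists them. SAP 8.1.2 has a deviation category for receipt of an excluded medication. SAP 6.2 defines the per-protocol (PP) set as ITT subjects without a major protocol violation, fixed before unblinding. SAP 8.2 makes PP the primary efficacy set and ITT the supportive one.

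**The concern.** The trial compares 0, 45 and 90 mg/day of an extract of these botanicals, and the protocol does not treat the separate ingredients as inert. Section 1.4 concludes that all three contribute to the neuroprotective effect. It also attributes part of the in-vitro MAO-B inhibition to paeonol from MC and imperatorin from ADR. Starting an MAO-B inhibitor is prohibited, while the source botanicals are not mentioned.

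Intake from outside the study would give a placebo subject some of the test material, and would give a subject on active drug an unmeasured addition. That touches the safety and tolerability comparison, which is the primary objective, as well as efficacy. The PP restriction cannot remove such subjects if no rule has been broken, and the compliance check in Section 6.9 counts study tablets only.

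This goes beyond the general point that trial subjects take supplements. The background section reports the test article's own ingredients on sale in the country where the trial runs, and the operative sections do not act on it.

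**Working it through.** **Step 1: which uses are covered.** Four cases, by reason and timing, for a product containing MC, BF or ADR:

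| Use | Provision that reaches it | Result |
|---|---|---|
| At screening, for Parkinson's disease | Inclusion 3 | Arguably ineligible |
| Started on study, for Parkinson's disease | Opening sentence of Section 7; 7.1 item 1, whose drug classes are given as examples | Arguably prohibited |
| At screening, for another reason | None; exclusion 8 reaches only investigational products | Eligible, may continue |
| Started on study, for another reason | None | No deviation |

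The last two rows are not far-fetched. Section 1.4 gives headache, cold, insomnia, constipation, cough and indigestion among the uses of these products.

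**Step 2: what follows for the analysis sets.** The excluded-medication category in SAP 8.1.2 depends on the protocol's lists, which omit the botanicals. A subject in either of the last two rows therefore has no major violation on this account and stays in the PP set.

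**Step 3: size.** The plan gives no figure to reproduce. Protocol 9.3 and SAP 4 set 20 subjects per group by clinical judgment, with no effect size, SD or power, and no prevalence of supplement use is stated. What can be shown is how any effect depends on unknowns. Let:

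- δ = mean difference between active and placebo among non-users
- f_P, f_A = share of users in the placebo and the active arm
- e = effect of the supplement as a fraction of δ
- use starting after baseline

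If effects add, the expected difference is δ(1 + e·f_A) − δ·e·f_P = δ[1 − e(f_P − f_A)].

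- e = 1, f_A = 0, f_P = 1/20: δ × 0.95, a 5% dilution
- e = 1, f_A = 0, f_P = 3/20: δ × 0.85, a 15% dilution
- e = 0.5 (assumed), f_A = 0, f_P = 1/20: δ × 0.975, a 2.5% dilution
- f_P = f_A: no dilution in expectation
- f_A greater than f_P: the difference is enlarged

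If the response saturates, so that users on active drug gain nothing further, the expected difference is δ(1 − e·f_P) whatever f_A is. The 1/20 assumes that all 20 placebo subjects are analysed; with n analysed it becomes 1/n.

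**Step 4: steady users.** A supplement effect s that is present at both Day 0 and week 12 drops out of the raw change. Under the ANCOVA in SAP 8.2.1 the subject's adjusted change keeps (1 − β)s, where β is the slope of the week-12 score on the baseline score. That is small if β is near 1. The documents give neither s nor β.

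**The case against.** The case on the other side narrows the point in four ways.

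- **Use for Parkinson's disease is arguably barred.** This stands. A reader might infer that any subject can take these products and remain compliant. The first two rows of the table do not support that.
- **A supplement is not the test product.** This stands. Section 1.4 speaks of MC, BF *or* ADR in US supplements, calls DA-9805 the first mixture of all three, and reports effects stronger than those of the single extracts. Table 6-1 specifies a 1:1:1 extract in 90% ethanol. A reader might infer that a placebo subject could in effect take study drug. The documents support only one or more ingredients in an unknown preparation.
- **Recording is already required.** This largely stands. All medications and therapies are documented, over-the-counter use is asked about at each visit, and Section 1.4 describes some of these products as over-the-counter herbals. A reader might infer that use would go unrecorded, but a recording route exists. What remains is that the visit question does not name supplements, so capture depends on whether the subject thinks of the product as a medication.
- **Randomisation and baseline adjustment limit the bias.** This stands in part. Equal use cancels in expectation only if effects add, and with 20 per arm chance imbalance is possible. Steady use mostly drops out of change from baseline, whereas use begun on study does not.

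None of this closes the gap. Recording a product does not restrict it and does not create a deviation.

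**Conclusion.** The concern holds in a limited form. Section 1.4 reports US supplements containing the trial's own botanicals, and Sections 3.1.3 and 7.1 do not deal with them. A subject in any arm who uses one for a reason other than Parkinson's disease breaks no written rule and stays in the primary efficacy population.

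The effect on the comparison cannot be quantified from the documents. The 5% per placebo user is an upper bound that rests on three assumptions: a supplement as effective as DA-9805 (and no more so), use on placebo only, and use begun after baseline. It also takes 20 analysed subjects. A reader might infer a loss of 5% to 15% in the treatment difference. The documents establish none of the three assumptions, and the 0 to 3 users behind that range are themselves assumed. A reader might also infer that earlier use contaminates the baseline through carry-over. This first-in-human protocol reports no human pharmacokinetics, so that cannot be shown.

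The point is worth correcting because the correction is cheap and specific to this test article, and because use that was never recorded cannot be recovered afterwards.

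**What to change.** 1. **Protocol 3.1.3 and 7.1 (and the synopsis).** Reconcile these with Section 1.4 so that products containing MC, BF or ADR are covered by the eligibility and prohibited-product lists. The sponsor should set any period before Day 0 and the handling of users. That includes saying how the Section 5.2 withdrawal reason for prohibited medication would apply.
2. **Protocol 7 and the CRF.** Add dietary and herbal supplements to the visit question and to the CRF prompt.
3. **SAP 8.1.2 and 6.2.** Count on-study use of such products under the excluded-medication category when the PP set is identified before unblinding. The by-arm summary in SAP 8.1.4 can then show how many users there were in each group, which the formula in the working needs.

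The cost is a short protocol amendment, one CRF prompt and a sentence or two in the SAP. A few supplement users would be screened out or leave the PP set. Leaving the PP set would depend on behaviour after randomisation, so the ITT analysis already planned as supportive should be read alongside it.
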